10.0 EVALUATION DURING TREATMENT/INTERVENTION

During concurrent temozolomide and radiotherapy:

- CBC every week.
- Brief physical exam weekly by radiation oncology.
- Contrast enhanced MRI (including perfusion) at the completion of radiotherapy and prior to initiation of adjuvant therapy – this will be considered a new baseline MRI and all patients may continue to adjuvant temozolomide.

During adjuvant temozolomide:

- CBC every week
- Monthly exam
- Contrast enhanced MRI (including perfusion) after every 2 cycles of therapy patients with evidence of tumor progression as compared to the post radiotherapy MRI will be removed from the study.
- Monthly comprehensive chemistry panel.

During maintenance cis-retinoic acid:

- Approximately monthly exam for 6 months then approximately every 2-3 months thereafter.
- Monthly CBC, comprehensive chemistry panel and lipid panel.
- Contrast enhanced MRI (including perfusion) after every 2-3 cycles of therapy patients with evidence of tumor progression as compared to the post radiotherapy MRI will be removed from the study.

IRB#: 05-079 A(17)

MGMT analysis:

Unless MGMT analysis was already performed as part of routine care at MSKCC or an MSKCC designated laboratory, *MGMT* methylation analysis will be performed by real-time PCR using TaqMan machine via OncoMethylome Sciences SA. Ten paraffin slides (around 10 micron), heated or baked (maybe less than 65C) per patient will be required. DNA will then be isolated and modified for real-time PCR on modified DNA. The final result will be the relative ratio of *MGMT* methylation / beta-actin as compared with positive control coming with the DNA modification kit.

[name], (Project Coordinator NA) should be contacted before any shipment. Samples must arrive during business hours from Monday through Friday and shipped overnight to:

OncoMethylome Sciences SA

Attn: [name]

[name]

[name]

[name]

[contact]

Contact information for [name]:

[contact]

[contact]

Email: [contact]

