8.0 PRETREATMENT EVALUATION

The following studies are required within two weeks prior to starting concurrent chemotherapy and radiotherapy:

• Complete history and physical exam including neurologic exam.

IRB#: 05-079A(17)

- Height and weight.
- CBC including WBC differential and platelet count.
- Comprehensive chemistry panel.
- Contrast enhanced MRI scan of the Brain* (this scan should ideally be performed within 72 hours of surgery and does not need to be repeated within the two weeks prior to treatment onset)

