9.0 TREATMENT/INTERVENTION PLAN

9.1 Concurrent temozolomide and radiotherapy

This treatment should start within 6 weeks of surgical resection.

Standard focal external beam radiotherapy will be delivered using conventional radiation planning (3D conformal). The total dose should be approximately 6000 cGy (+/- 5%). Stereotactic boost is not allowed. Patients may receive their radiotherapy at MSKCC or locally provided that treatment planning and summary is available.

Temozolomide will be given at a dose of 75mg/m2 daily for the complete course of radiotherapy. Patients will start temozolomide the night before they receive the first dose of radiotherapy and take the last dose on the final day of radiotherapy. Patients will dose on weekends and holidays when radiotherapy is not scheduled. Supportive anti emetic therapy will be prescribed per institutional guidelines or at the discretion of the treating physician.

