9.2 Randomized adjuvant therapy

This therapy will begin 2- 4 weeks after the completion of radiotherapy and will last for a total of 6 cycles (1 cycle = 28 days). Patients will be randomized to receive dose dense or metronomic temozolomide on the basis of histology and KPS.

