9.22 Metronomic temozolomide

Temozolomide 50mg/m² will be given to patients on days 1-28 of each 28 day cycle. Supportive anti-emetic therapy will be prescribed per institutional guidelines or at the discretion of the treating physician. Growth factors may be used to treat low blood counts but may not be given prophylactically.

9.3 Maintenance cis-retinoic acid.

This therapy will start at the completion of 6 cycles of adjuvant temozolomide in all patients who have had no clinical or radiographic evidence of tumor progression. Treatment will continue in 28 day cycles until tumor progression.

13-cis retinoic acid 100 mg/m^2 will be given on days 1-21 of each 28 day cycle. (Minor variations in dose are allowed given limited pill strength options). On the first cycle patients may be given a titrated dose to evaluate tolerability.

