11.0 TOXICITIES/SIDE EFFECTS

Temozolomide: the most common grade 3 or 4 toxicities reported include:

- <10%: nausea/vomiting, elevated liver enzymes, elevated BUN/Cr, constipation.
- <5%: lymphopenia, thrombocytopenia, rash, headache, alopecia, fatigue.
- <1%: lethargy.

NCI CTC version 3.0 will be used to grade all toxicity.

If hematologic toxicity grade 3 or higher occurs patients may be treated with appropriate growth factors. If clinically indicated the dose of temozolomide may be reduced by 25%.

If grade 3 or 4 treatment related non-hematologic toxicity occurs the dose of temozolomide may be reduced by 25%. Temozolomide should be held until all related non hematologic toxicity has resolved to a grade 2 or lower.

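### No blood chemistry is scheduled during concurrent temozolomide or before adjuvant cycle 1, so the section 11 hold has no scheduled trigger there for liver or kidney laboratory toxicity

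*Combined protocol and SAP*

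**What the plan says.** Section 8.0 asks for a comprehensive chemistry panel at baseline: "The following studies are required within two weeks prior to starting concurrent chemotherapy and radiotherapy". That sample precedes all study drug.

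Section 9.1 then sets the concurrent dose: "Temozolomide will be given at a dose of 75mg/m2 daily for the complete course of radiotherapy". Dosing runs from the night before the first fraction to the day of the last, including weekends and holidays. Section 9.2 says of the adjuvant phase: "This therapy will begin 2- 4 weeks after the completion of radiotherapy". Neither section sets a laboratory criterion for starting adjuvant treatment.

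In section 10.0, the list under "During concurrent temozolomide and radiotherapy" has three items: a CBC each week, a brief weekly exam by radiation oncology, and a contrast MRI after radiotherapy and before adjuvant therapy. The adjuvant list adds "Monthly comprehensive chemistry panel", and the maintenance list also has a monthly panel.

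Section 11.0 lists the most common grade 3 or 4 temozolomide toxicities, with this as the highest band: "<10%: nausea/vomiting, elevated liver enzymes, elevated BUN/Cr, constipation". Its rule for non-hematologic toxicity is "Temozolomide should be held until all related non hematologic toxicity has resolved to a grade 2 or lower". The rule is not limited to any treatment phase.

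**The concern.** Raised liver enzymes and raised BUN or creatinine can be graded only from a blood chemistry. A CBC, a brief exam or an MRI cannot show them. The protocol names these two toxicities and tells the investigator what to do about them, but for the whole concurrent phase it schedules no test that could reveal them. It also lets adjuvant treatment begin without a result.

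What is at stake is patient safety. A patient with an asymptomatic grade 3-4 elevation during radiotherapy could go on taking temozolomide every day and then start one of the two adjuvant regimens. Section 6.1 admits patients with SGOT up to 2.5 times the upper limit of normal, and creatinine and bilirubin up to twice it, so some may enter with abnormal values that are not rechecked on schedule. Section 9.1 also lets patients have radiotherapy locally, so routine practice at the sponsoring institution is a weak substitute for a listed test.

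A lesser consequence is that transient, asymptomatic laboratory events in this phase may be missing from the toxicity tabulation in section 14.2.

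**Working it through.** The plan gives no figure to reproduce. The check compares the schedule with the hold rule and then sizes the unmonitored interval.

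**Schedule by phase (sections 8.0, 9.1-9.3 and 10.0)**

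| Phase | Temozolomide | Blood tests listed | Scheduled chemistry |
|---|---|---|---|
| Baseline | none | CBC, chemistry | 1 panel |
| Concurrent | 75 mg/m2 daily | weekly CBC | none |
| Break of 2-4 weeks | none | none | none |
| Adjuvant, metronomic | 50 mg/m2 daily | weekly CBC, monthly chemistry | monthly |
| Adjuvant, dose dense | 150 mg/m2, 14 of 28 days | weekly CBC, monthly chemistry | monthly |
| Maintenance (retinoid) | none | monthly CBC, chemistry and lipids | monthly |

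**Length of the concurrent phase.** Section 9.1 gives about 6000 cGy (±5%) without a fraction size. Assume 200 cGy per fraction, as in the reference regimen described in section 3.1, at five fractions per week:

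- 6000 / 200 = 30 fractions; 30 / 5 = 6 weeks, which agrees with the six weeks section 3.1 gives for that regimen.
- Monday start: 5 × 7 + 5 = 40 calendar days of radiotherapy, plus the night before = 41 doses.
- Start on another weekday: 6 × 7 = 42 days, plus the night before = 43 doses.

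**Exposure without a scheduled panel**

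- Concurrent: 41 × 75 = 3075 mg/m2 to 43 × 75 = 3225 mg/m2, with 0 panels.
- One metronomic cycle (50 mg/m2 "given to patients on days 1-28 of each 28 day cycle"): 28 × 50 = 1400 mg/m2, with one monthly panel.
- One dose-dense cycle: 14 × 150 = 2100 mg/m2, with one monthly panel.

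**Is this a lower-dose phase?**

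- Against metronomic: 75 / 50 = 1.5 times the daily dose.
- Against dose dense, averaged over the cycle: 2100 / 28 = 75 mg/m2 per day, the same as concurrent. On its dosing days the dose-dense arm receives 150, twice the concurrent dose.

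The cumulative ratios are 3075/1400 to 3225/1400 = 2.2-2.3 (metronomic) and 3075/2100 to 3225/2100, about 1.5 (dose dense). They mix dose with duration. Duration alone contributes 41/28 to 43/28, about 1.5, which is all of the dose-dense ratio and part of the metronomic one.

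**Interval without a required panel, counted from first dose**

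- To the first adjuvant dose: 6 + 2 = 8 to 6 + 4 = 10 weeks, about 6 of them on drug.
- To the end of adjuvant cycle 1: 8 + 4 = 12 to 10 + 4 = 14 weeks. This applies only if the first monthly panel is drawn at the end of cycle 1. Section 10.0 gives no day.

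The baseline panel may be up to two weeks older still, so the last chemistry result may be 8-12 weeks old on adjuvant day 1.

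**The case against.** The strongest reply is that nothing in the plan is contradicted. Section 11.0 is conditional: it says what to do if a toxicity occurs and does not promise a scheduled test for each one in every phase. The hold applies however the toxicity is found, and the weekly exam gives an occasion to order chemistry. Entry limits and a recent baseline panel exclude patients with marked abnormality at the start. That all stands, but it reduces the gap without closing it: an asymptomatic elevation gives no prompt for a test.

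A second reply is that no harm has been shown. The band of under 10% is an upper limit for temozolomide in general, not a rate at 75 mg/m2. For the phase III regimen that used the same concurrent dose, section 3.1 reports good tolerance and names myelosuppression and fatigue as the grade 3 or higher events. This stands to the extent that no count of missed events can be given. It does not show that liver or kidney events are absent, and section 11.0 itself puts them in a higher band than thrombocytopenia (under 5%), which is checked weekly.

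A third reply is that the cumulative-dose comparison flatters the concern, because a six-week phase is set against four-week cycles. That is fair. The point rests on dose per day, where the concurrent phase is 1.5 times metronomic and equal to the dose-dense average.

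Finally, the monthly adjuvant panel could be drawn on day 1 of cycle 1. It could, but the text neither says so nor requires a result before dosing, whereas it does place the MRI before adjuvant therapy starts.

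**Conclusion.** The concern holds. Followed as written, the plan gives about six weeks of daily temozolomide at 75 mg/m2, and allows adjuvant treatment to start, with no scheduled test that could trigger the hold for liver enzyme, BUN or creatinine elevation. No other section fills the gap, and no reason is given for leaving chemistry out of this phase alone.

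The omission itself rests on the text. The 41-43 doses and the 8-10 weeks rest on the assumed 30 fractions at five per week. The frequency of missed events is unknown.

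The finding is limited to scheduled tests and to these laboratory toxicities; the hold still works for clinically evident toxicity and for anything found by prompted testing. The one-year survival endpoint and the comparison of arms are not systematically affected, because both arms share the same concurrent phase. This is a safety-schedule gap that should be corrected, not a threat to the trial's conclusions.

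**What to change.** Make two additions to the protocol:

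1. In the concurrent-phase list of section 10.0, add a comprehensive chemistry panel every 2-4 weeks, taken with a weekly CBC draw.
2. In section 9.2 or 10.0, require a chemistry result before the first adjuvant dose.

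The cost is two protocol lines and about 2-4 routine panels per patient: 1-3 over a six-week course plus 1 before adjuvant cycle 1. The concurrent panels need no extra venipuncture.

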14.2 Secondary endpoints include progression-free survival defined as the date of study entry to the first scan that demonstrates tumor progression (please note that the MRI after completion of radiotherapy will be used as the baseline scan for response assessment). Frequency of toxicity will be tabulated according to the NCI Common Toxicity Criteria (version 3.0). Methylation *MGMT* status will be assessed using real-time PCR. A Fishers exact test will be used to compare one year survival by MGMT status (methylated/unmethylated) in order to observe any trends similar to that from the retrospective EORTC/NCIC.

In addition, these regimens will be administered to forty patients with all other malignant glioma subtypes. Up to twenty patients in each arm will be accrued. Endpoints such as one-year survival probability, overall survival and progression-free survival will be computed in order to gain preliminary data for these other subtypes.

The minimum anticipated sample size would be 66 patients (23 in each cohort plus 20 patients with other malignant glioma subtypes.) If both cohorts accrue patients to the second stage then a total of 118 evaluable patients will be accrued (39 in each cohort + 40 patients with other malignant glioma subtypes). To ensure 118 evaluable patients, we will accrue 140 patients to guard against a 20% rate of ineligibility and patient drop out observed during an interim analysis. Patients who withdraw consent or are found to be ineligible can be replaced. The anticipated rate of accrual is 6 patients/month requiring 12-18 months to complete the accrual to the trial.

14.3 RANDOMIZATION:

Patients will be randomized to dose dense temozolomide or metronomic temozolomide. After eligibility is established and immediately after consent is obtained, patients will be registered in the Protocol Participant Registration (PPR) system and randomized using the Clinical Research Database (CRDB), by calling the MSKCC PPR registry at [contact] between the hours of 8:30 am and 5:30 pm, Monday - Friday. Randomization will be accomplished by the method of random permuted block, and patients will be stratified by KPS (<80 vs \geq 80).

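### MRI is scheduled by treatment cycle, with an unruled choice of 2 or 3 cycles in maintenance, so the recorded date of progression (secondary endpoint PFS) can shift for reasons unrelated to efficacy

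*Combined protocol and SAP*

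**What the plan says.** Section 14.2 names "progression-free survival defined as the date of study entry to the first scan that demonstrates tumor progression" as a secondary endpoint. Section 12.0 defines progression by lesion size or a new tumor site, so the event is found on a scan.

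Section 10.0 sets the scans. In the adjuvant phase the rule is "Contrast enhanced MRI (including perfusion) after every 2 cycles of therapy"; in maintenance it is "Contrast enhanced MRI (including perfusion) after every 2-3 cycles of therapy". Sections 9.2 and 9.3 make a cycle nominally 28 days in both phases, so these are 8 weeks, and 8 to 12 weeks, if nothing is delayed. No section gives a scan date, a window, a rule for choosing 2 or 3, or an instruction for scanning during an interruption. Other assessments in section 10.0, such as blood counts and examinations, are set by the week or month.

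On interruptions, section 11.0 says after grade 3 or 4 related non-hematologic toxicity: "Temozolomide should be held until all related non hematologic toxicity has resolved to a grade 2 or lower". It gives no time limit and does not say whether the cycle count, and with it the scan, moves.

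The arms differ in schedule (sections 9.21 and 9.22). The documents describe neither blinding nor independent reading of scans.

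**The concern.** An endpoint dated to a scan inherits the scan schedule. If the schedule follows cycles, and cycles slip, a patient with the same disease course is scanned later and is credited with longer PFS. If the maintenance interval is chosen case by case by someone who knows the arm, it can also come to differ by arm. Either route could make the regimens look different on PFS when they are not. PFS is the first secondary objective in section 2.0 and is also to be computed for the other glioma subtypes (section 14.2). Analysis can allow in part for irregular scan dates, but it cannot recover scans that were not done.

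**Working it through.** **The plan's own figures.** The documents give no precision or power for PFS. The design figure they do give, the two-stage rule of section 14.1 (23 then 16 patients; continue with at least 12 alive; success with at least 24 of 39 alive), was recomputed with exact binomial probabilities. The type I error is 0.098 at 50% one-year survival and the power is 0.902 at 70%, within the stated 0.10 and 0.10. Scan dates do not enter this calculation.

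**Step 1: interval length.** 2 × 28 days = 8 weeks; 3 × 28 days = 12 weeks. If progression falls evenly between scans, mean delay to detection is half the interval: 8/2 = 4 weeks and 12/2 = 6 weeks, a difference of 2 weeks.

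**Step 2: one patient.** Count weeks from the start of maintenance, with scans at 8, 16, 24 or at 12, 24:
- progression in weeks 0–8: found at 8 or 12, shift +4
- weeks 8–12: found at 16 or 12, shift −4
- weeks 12–16: found at 16 or 24, shift +8
- weeks 16–24: found at 24 on both, shift 0

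Mean = (8×4 − 4×4 + 4×8 + 8×0)/24 = 48/24 = 2 weeks. The range is −4 to +8 weeks.

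**Step 3: whole arms at different maintenance intervals.** Assumptions not in the documents: adjuvant therapy starts 10 weeks after entry, progression times are exponential, and true PFS is identical in both arms. Adjuvant scans then fall at weeks 18, 26 and 34, and maintenance scans at 42, 50, 58 (8-weekly) or 46, 58, 70 (12-weekly). A patient counts as progression-free at week 52 if true progression comes after the last scan before week 52, which is week 50 or week 46. With median m in weeks, observed 12-month PFS is 2^(−50/m) or 2^(−46/m):

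| True median | 8-weekly | 12-weekly | Spurious HR |
|---|---|---|---|
| 7 months | 31.9% | 35.0% | 0.969 |
| 9 months | 41.1% | 44.2% | 0.971 |
| 12 months | 51.4% | 54.2% | 0.975 |

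The hazard ratios come from a Cox model fitted to the scan-dated times. Over true medians of 6 to 15 months, the observed median moves by 0 to 0.9 months, depending on where it falls on the scan grid.

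**Step 4: holds, if they delay later cycles.** Assume one arm loses 2 weeks per 2 adjuvant cycles (one week per cycle, so 2 × 5 = 10 weeks between scans). Scans move to weeks 20, 30 and 40. The spurious hazard ratio is 0.943, 0.969 and 0.987 at true medians of 7, 9 and 12 months. At 7 months the observed median moves from 7.85 to 9.23 months; at 9 months it moves the other way, from 9.69 to 9.23. With holds and the 12-week interval in the same arm, the hazard ratio is 0.90 to 0.95.

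**Step 5: against sampling error.** With 39 patients per arm and PFS near 50%, the standard error of a difference is √(2 × 0.25/39) = 0.113, about 11 points. A 3-point shift is about a quarter of that.

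**The case against.** The strongest reply is that little hangs on this. Each cohort is judged on one-year survival against a fixed 50%, and if both succeed the one with the higher one-year survival goes forward (section 14.1). No between-arm PFS test is planned. All of that stands. A reader might infer that PFS would serve as the main supporting evidence, or the tie-breaker, if survival were similar in the two arms; the documents give it no such role.

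A reader might also infer that holds necessarily postpone scans. The documents do not say so. Cycles are defined as 28 days, section 15.2 speaks of 6 months of post-radiation chemotherapy, and under continuous dosing a hold could simply use up days within a cycle. The mandatory hold concerns non-hematologic toxicity only, and a week lost in every cycle is an extreme case. What remains is that the text allows either reading, and only one of them keeps the scan on the calendar.

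Third, a reader might infer that one arm will in fact be scanned less often. In maintenance both arms receive the same drug under the same allowance, and nothing suggests that clinicians would treat them differently. If the choice is unrelated to arm, it adds noise rather than between-arm bias. This also stands: the schedule permits a difference, but does not show one.

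**Conclusion.** The point holds as a minor weakness in how a secondary endpoint is ascertained. The text ties the PFS date to scans whose timing is neither anchored to the calendar nor fully specified, in a trial where knowledge of the arm can be inferred from the visibly different schedules and the absence of any described blinding.

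The 2-week mean delay and the −4 to +8 week range follow from the stated cycle lengths, with progression spread evenly between scans. The hazard ratio of about 0.97 and the 3 points on 12-month PFS further assume a complete split of the maintenance interval by arm, exponential progression and an adjuvant start at week 10. The larger values require frequent holds, confined to one arm, that delay its later cycles. The documents give no figure for holds or scan intervals by arm, so any actual difference between arms is an assumption. The primary endpoint, the Simon design and the selection between arms are not affected.

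**What to change.** In section 10.0, schedule MRI by calendar: every 8 weeks from day 1 of adjuvant therapy (the present nominal interval), whatever the holds or delays. In maintenance, use one fixed calendar interval, chosen by the sponsor within the present 8 to 12 weeks. Apply the same schedule in both arms, with a window of about 1 week. The toxicity rules in section 11.0 need not change for this purpose.

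The cost is protocol wording, less scheduling freedom and a few scans that no longer fall on a cycle boundary. The number of scans stays about the same, and no sample size or decision rule changes.

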11.0 TOXICITIES/SIDE EFFECTS

Temozolomide: the most common grade 3 or 4 toxicities reported include:

- <10%: nausea/vomiting, elevated liver enzymes, elevated BUN/Cr, constipation.
- <5%: lymphopenia, thrombocytopenia, rash, headache, alopecia, fatigue.
- <1%: lethargy.

NCI CTC version 3.0 will be used to grade all toxicity.

If hematologic toxicity grade 3 or higher occurs patients may be treated with appropriate growth factors. If clinically indicated the dose of temozolomide may be reduced by 25%.

If grade 3 or 4 treatment related non-hematologic toxicity occurs the dose of temozolomide may be reduced by 25%. Temozolomide should be held until all related non hematologic toxicity has resolved to a grade 2 or lower.

